12.8 Early Termination Visit

The Early Termination visit will occur on the date the subject withdraws from the study, even if the date does not correspond to a protocol-specific visit.

Page 104

If a subject leaves the study prior to the Week 260 visit, the subject will be asked to return to the study site and complete an Early Termination visit. At the Early Termination visit, as many of the following assessments as possible should be done:

- Physical examination
- Weight
- Assessment of Adverse Events and Concomitant Medications (including review of subject diary for bleeding and FVIII use)
- Vital Signs
- Blood chemistry, hematology, and coagulation tests (refer to Table 9.7.8.2.1)
- Urine Tests (refer to Table 9.7.8.2.1)
- Liver Tests (refer to Table 9.7.8.3.1)
- FVIII Assays
 - o FVIII activity level (chromogenic substrate FVIII assay)
 - o FVIII activity level (one-stage clotting FVIII assay)
 - FVIII coagulation activity exploratory assay
 - o Bethesda assay (with Nijmegen modification) for FVIII inhibitor level
 - o FVIII protein assay
- AAV5 TAb Assay
- AAV5 TI Assay
- FVIII antibody titer
- Exploratory biomarker assessments
- PBMC collection
- VWF:Ag
- TGA Assay
- PCR of vector DNA in blood, saliva, urine, semen, and stools
 - Sample testing at the ETV is not required if at least 3 consecutive samples were clear during the Post-Infusion Follow-Up period.
- Haemo-QoL-A assessment
- EQ-5D-5L
- HAL

Page 105

- WPAI+CIQ:HS
- PROBE

12.9 End of Study

The study will end after the last subject yet to complete the last Long-Term Follow-Up visit (Week 260) does so, has transferred to another BMN 270 study, is withdrawn from the study, or discontinues from the study. BioMarin reserves the right to discontinue the study any time for clinical or administrative reasons and to discontinue participation of an individual Investigator or site for clinical or administrative reasons, including, but not limited to, poor enrollment or noncompliance with procedures of the protocol or GCP. In addition, the study may be terminated if, in the opinion of BioMarin, the safety of the study subjects may be compromised.

Page 106

13 DATA QUALITY ASSURANCE

BioMarin personnel or designees will visit the study site prior to initiation of the study to review with the site personnel information about the IP, protocol and other regulatory document requirements, source document requirements, eCRFs, monitoring requirements, and procedures for reporting AEs, including SAEs.

At visits during and after the study, a CRA will monitor the site for compliance with regulatory documentation, with a focus on accurate and complete recording of data on eCRFs from source documents, adherence to protocol, randomization (if applicable), SAE reporting and drug accountability records.

Data quality control and analysis will be performed by BioMarin or a designee, based on a predefined analysis plan.

Page 107

14 STATISTICAL METHODS AND DETERMINATION OF SAMPLE SIZE

14.1 Statistical and Analytical Plans

The statistical analysis plan (SAP) will provide additional details on the planned statistical analysis. Unless otherwise stated, all analyses will be performed using SAS.

14.1.1 Interim Analyses

An interim analysis is planned after approximately 20 treated HIV-negative subjects have completed the Week 26 visit (or have discontinued study participation prior to Week 26). Data will be reviewed by the DMC, based on the SAP, and a formal recommendation will be made whether to continue the study as designed.

The primary efficacy endpoint for the interim analysis involves hFVIII activity, as measured by chromogenic substrate assay, achieved post-BMN 270 infusion.

The fallback procedure (Wiens, 2005) will be used to adjust for multiplicity of the interim analysis at Week 26 and the final analysis at Week 52 (regardless of the interim analysis results, the study is planned to continue upon the DMC's recommendation, and the final analysis will be performed at Week 52). At the final analysis at Week 52, the secondary efficacy endpoints will be tested hierarchically; the level of significance will be determined by the fallback procedure.

The secondary and tertiary endpoints will be summarized descriptively at the interim (Week 26) analysis.

The details of the interim analysis, including the control of Type I error rate, will be specified in the SAP.

14.1.2 Procedures for Accounting for Missing, Unused and Spurious Data

Because the completeness of the data affects the integrity and accuracy of the final study analysis, every effort should be made to ensure complete, accurate, and timely data collection and, therefore, avoid missing data.

Missing data imputation and sensitivity analyses to assess the impact of missing data on the primary and secondary efficacy endpoints analyses are described in the following sections. Additional details regarding the handling of missing data will be provided in the SAP.

14.2 Primary Efficacy Endpoint

For the primary efficacy endpoint at Week 52 (ie, the change in the hFVIII activity during Weeks 49-52 post-BMN 270 infusion from baseline, as measured by chromogenic substrate

Page 108

assay), a one-sample t-test will be used to test the null hypothesis that the change is 0 or less against the alternative hypothesis that the change is greater than 0. Descriptive summaries of the proportions of subjects whose FVIII activity during Weeks 49-52 is greater than or equal to select thresholds, such as 15, 25 and 30 IU/dL, and the confidence intervals of the proportions will also be provided.

For a subject with a missing value of the primary endpoint, the median value in the subject's last 4-week window containing a valid observation will be used. Additional analyses will be conducted to examine the sensitivity of the results to the handling of missing data, including analysis using observed cases, and a mixed model for repeated measures (MMRM) approach. Further detail will be provided in the SAP.

The analyses for the primary endpoint will be performed using the analysis populations as defined in Section 14.8.

14.3 Secondary Efficacy Endpoints

The primary analyses for the secondary endpoints will be performed on the 110 subjects in the mITT population who will be followed up for approximately 6 months in the non-interventional study 270-902 prior to their enrollment in 270-301. The baseline values will be derived from the prospectively collected data in 270-902.

For the first secondary efficacy endpoint at Week 52 (ie, the change in the annualized utilization (IU/kg) of exogenous FVIII replacement therapy during Weeks 5-52 post-BMN 270 infusion from baseline), a one-sample t-test will be performed to test the null hypothesis that the change is 0 or greater against the alternative hypothesis that the change is less than 0. The missing value of the change will be imputed as 0.

For the second secondary efficacy endpoint at Week 52 (ie, the change in ABR, annualized bleeding rate, during Weeks 5-52 post-BMN 270 infusion from baseline), a one-sample t-test will be performed to test for non-inferiority of BMN 270 against FVIII prophylaxis (ie, the baseline ABR calculated using subjects' data collected as part of 270-902) using a non-inferiority margin of 3.5, ie, to test the null hypothesis that the change is 3.5 or greater against the alternative hypothesis that the change is less than 3.5. If non-inferiority is demonstrated, the test for superiority of BMN 270 against FVIII prophylaxis will be performed. The missing value of the change will be imputed using the median value of the changes of all observed cases.

A sensitivity analysis is planned to analyze ABR using a generalized linear mixed model assuming negative binomial as the underlying distribution. The model will include period (pre- to post-BMN 270 infusion) as the only factor. The actual number of bleeding episodes

Page 109

will be used as the independent variable with the time period adjustment (animalization) being implemented as the offset.

To assess the impact of missing data, analyses using observed case are planned as sensitivity analyses for the secondary endpoints. Multiple imputation methods may also be performed.

The primary and secondary efficacy hypotheses will be tested hierarchically according to the order described above. Multiple comparison procedures will be described in greater detail in the SAP.

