For the analytic sample size calculation of the second secondary endpoint, ABR, it is assumed that the pre- and post-BMN 270 infusion population mean ABRs are 3.5 and 1 respectively, and the distribution of ABRs is negative binomial distribution with a dispersion parameter of 2.2. Given the underlying negative binomial distributions, the standard deviations of the pre- and post-BMN 270 infusion ABRs are calculated as 7.8 and 1.8 respectively. The mean (SD) of the change from the pre- to post-BMN 270 infusion ABRs are calculated as -2.5 (8) assuming the correlation between pre- and post-BMN 270 infusion ABRs is zero. Under this assumption, an analytic sample size of 110 will also have at least 95% power to demonstrate that the change in the annualized number of bleeding episodes requiring exogenous FVIII replacement treatment (ABR) during Week 5 to Week 52 of the study post-BMN 270 infusion from the baseline ABR is less than 3.5 (non-inferiority margin), using a one-sample t-test with a 2-sided significance level of 0.05. Under the same assumptions, a sample size of 110 will have approximately 90% power to

Page 111

demonstrate that the change is less than 0, ie, superiority of BMN 270 against FVIII prophylaxis.

Overall, the planned sample size will have greater than 80% power for testing the primary and secondary efficacy endpoints hierarchically at the final analysis with a 2-sided significance level of 0.05.

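### Filling every missing ABR change with the median observed change makes the standard error too small and raises the non-inferiority error by an amount that grows with dropout

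*Protocol*

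**What the plan says.** Section 14.3 (Amendment 4) tests the change in ABR with a one-sample t-test, first for non-inferiority and then for superiority. The non-inferiority test is "to test the null hypothesis that the change is 3.5 or greater against the alternative hypothesis that the change is less than 3.5". On the analysis set it says "The primary analyses for the secondary endpoints will be performed on the 110 subjects in the mITT population", meaning those followed beforehand in the non-interventional study. The missing-data rule is "The missing value of the change will be imputed using the median value of the changes of all observed cases". For the other secondary endpoint, FVIII use, the same section says "The missing value of the change will be imputed as 0".

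Section 14.1.2 places the imputation rules in these endpoint sections and leaves only further detail to the SAP, so the rule is fixed here. Section 14.3 commits to observed-case sensitivity analyses and leaves multiple imputation optional. Section 9.3.4 says treated subjects who withdraw are not replaced. No dropout rate is given, and nothing says when an annualized change counts as missing.

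Section 14.3 of Amendment 6 is not in the part of the protocol at hand. The summary of that amendment says the statistical methods for the final efficacy analysis are unaffected, so the rule presumably still applies.

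**The concern.** A single value taken from the observed subjects adds no spread, yet each filled subject counts in the t-test as a full observation. The standard deviation shrinks and the sample size does not, so the test statistic is too variable for its reference distribution even when data are missing purely by chance.

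A second effect applies at the non-inferiority boundary. If mean ABR really rose from 3.5 to 7, the changes would be right-skewed counts whose median lies well below the mean. The fill then moves the estimate toward the claim.

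At stake is the error rate of a confirmatory, hierarchically tested claim. It would depend on how many subjects have no ABR change, a quantity that the protocol neither states nor limits.

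**Working it through.** **Inputs.** From Sections 14.3 and 14.7: n = 110; margin 3.5; test made "using a one-sample t-test with a 2-sided significance level of 0.05", so 2.5% in the tested direction; "population mean ABRs are 3.5 and 1 respectively"; "the distribution of ABRs is negative binomial distribution with a dispersion parameter of 2.2"; SDs before and after, "infusion ABRs are calculated as 7.8 and 1.8 respectively"; change -2.5 (SD 8) with zero correlation. The share missing is an assumption: 2% to 15%.

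**Step 1: the plan's own power.** SD of change = sqrt(7.8² + 1.8²) = 8.0. Standard error = 8/sqrt(110) = 0.763.
- Non-inferiority: (3.5 + 2.5)/0.763 = 7.9 standard errors, power above 0.999. The plan says at least 95%.
- Superiority: 2.5/0.763 = 3.28, power 0.901 by the noncentral t (0.906 by the normal approximation). The plan says approximately 90%.

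Both reproduce from the stated SD of 8. (A separate matter: mean 3.5 with dispersion 2.2 gives SD sqrt(3.5 + 2.2 × 3.5²) = 5.52. The stated 7.8 is sqrt(2) times that, without explanation.)

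**Step 2: standard error after the fill.** With k subjects filled at the centre of the observed data, the sum of squares is unchanged but is divided by n-1, and n stays at 110:

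reported SE / true SE = sqrt((n-k-1)/(n-1)) × sqrt((n-k)/n), about 1-d.

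For k = 11 (10%): sqrt(98/109) × sqrt(99/110) = 0.900. For symmetric data the one-sided error is then 1 - Φ(1.96(1-d)).

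**Step 3: the pull at the boundary.** With dispersion 2.2 in both periods and means 3.5 and 7, the change has mean 3.5, median about 1 and SD about 12.1. At 10% missing the expected filled mean is 0.9 × 3.5 + 0.1 × 1 = 3.25. That is 0.25 below the truth, or about 0.22 of a standard error (12.1/sqrt(110) = 1.15), in favour of non-inferiority.

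**Step 4: simulated one-sided error at the non-inferiority null.** 20,000 to 40,000 trials per case, n = 110, missing completely at random. Normal data: SD 8. Count data: negative binomial, dispersion 2.2. Ranges show the spread over separate runs.

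| Missing | SE ratio | Normal, formula | Normal, median fill | Count, median fill |
|---|---|---|---|---|
| 0% | 1 | 2.5% | 2.5% | 4.1% |
| 2% | 0.98 | 2.7% | 2.6% | about 4.5% |
| 5% | 0.945 | 3.1% | 3.1-3.3% | 5.4-5.8% |
| 10% | 0.900 | 3.9% | 3.8-4.1% | 6.9-7.6% |
| 15% | 0.854 | 4.8% | 4.6-4.8% | 9.1-9.4% |

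The observed-case test stays at about 2.5% for normal data and about 4.1% for count data throughout. The imputation effect is the distance from those values, not from 2.5%, in the count column. If the pre-infusion SD is instead matched to the stated 7.8, median fill gives 4.1% and 5.2% at 5% and 10% missing, against 3.1% for observed cases.

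**Step 5: a null-value fill.** Filling with 3.5 shrinks the numerator and the standard error by about the same factor. The simulated error is 3.8-4.2% for count data and 2.3-2.6% for normal data, which matches observed cases.

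**Step 6: superiority and power.** At the superiority null with count data, median fill gives 1.3% to 3.0% with up to 20% missing at random, against 1.4% to 2.5% with complete data (the range covers two count models). At the design values, non-inferiority power is about 1.00 with median, zero or margin fill.

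**The case against.** The strongest reply is that little may be missing. The endpoint is annualized over Weeks 5-52, so partial follow-up can yield a value, and the planned negative binomial sensitivity model already carries an exposure offset. Amendment 6 adds telephone collection of diary data when a visit fails. If only one, two or three of the 110 subjects had no value, the count-data error would be 4.4%, 4.6% or 4.8%, against 4.2% with none missing in the same run. This stands, and it limits the size of the problem. It does not settle the matter, because the protocol never says that partial follow-up is kept.

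Four stronger readings are tempting, and the documents do not support them.
- **Dropouts are credited with a typical benefit.** Under the design assumptions the change is left-skewed, with median between 0 and -1 against a mean of -2.5. The fill then gives less than the mean benefit. It is favourable near the non-inferiority boundary.
- **Bleeders leave, so the bias is larger.** If worse bleeders dropped out three times as often, the normal-data error at 10% missing would be 9.8%, against 6.3% for observed cases. Nothing in the protocol indicates such dropout. With recurrent bleeding, resumption of prophylaxis is discussed, and treatment failures stay in follow-up, with a reduced schedule only after Week 52.
- **The two fill rules contradict each other.** FVIII use has a null value of 0, whereas ABR non-inferiority has 3.5. Different rules for different hypotheses are not a contradiction.
- **The error reaches 6.5%, 8.0% and 9.8% at 5%, 10% and 15% missing even for normal data.** Those are two-sided rates and should not be set against the 2.5% that governs a one-directional claim.

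**Conclusion.** The point holds for the non-inferiority test. The fill understates the standard error by about the share missing and, at a skewed boundary, moves the estimate toward the claim. Under random missingness of 5%, 10% and 15%, it adds roughly 0.8, 1.3 and 2.3 percentage points for normal data (3.3%, 3.8% and 4.8% less 2.5%). For count data it adds about 1.3-1.7, 3.0 and 5.2 points (5.4-5.8%, 7.1% and 9.3% less 4.1%). At 2% missing the effect is about 0.2 to 0.4 points. The missing shares are assumed, and the count figures rest on dispersion 2.2 with mean ABR doubling to 7.

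Neither the observed-case sensitivity analysis nor optional multiple imputation corrects the main test. Superiority is not inflated by random missingness with count data, and non-inferiority power is near 1.00 if the design assumptions hold. A reader might infer that the ABR claim is unsafe as planned, but the documents do not support that. This is a should-fix: confirmatory error control ought not to depend on dropout being low when the remedy is a change of wording.

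**What to change.** - State that the ABR change is computed from each subject's observed bleeds and observed time after Week 5, so that partial follow-up is not missing. Define in the SAP how much time counts as usable.
- Only for a subject with no usable time after Week 5, replace the median with the null value of the test: 3.5 for non-inferiority and 0 for superiority. Multiple imputation with the same penalty is an alternative.
- Keep the observed-case analysis as a sensitivity analysis.

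The cost is protocol and SAP wording, a little programming and a slightly wider interval. Non-inferiority power stays at about 1.00 with up to 20% missing. Superiority power (normal, SD 8) with a zero fill is about 0.89 and 0.87 at 5% and 10% missing, against a nominal 0.91 with median fill. The observed-case test gives the same 0.89 and 0.87, so the difference is information that is really lost and that the median fill conceals. The fill must be specific to each test: using 3.5 in the superiority test would lower its power to 0.83 and 0.72 at those shares.

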14.4 Immunogenicity

Analysis of total and neutralizing antibody response and other immunological parameters will be primarily descriptive and involve both inter-subject and intra-subject comparisons.

14.5 Pharmacodynamic Analyses

Plasma FVIII protein concentrations and FVIII activities determined over the course of the study will primarily be evaluated and summarized with descriptive statistical measures (eg, mean, standard deviation, CV%, min, median, max).

14.6 Safety Analysis

The Medical Dictionary for Regulatory Activities terminology (MedDRA) will be used by the Sponsor to assign system organ class and preferred term classification to events and diseases, based on the original terms entered on the eCRF.

All AEs will be coded using the current version of MedDRA. The incidence of AEs will be summarized by system organ class, preferred term, relationship to study drug, and severity. A by-subject listing will be provided for those subjects who experience a serious AE (SAE), including death, or experience an AE associated with early withdrawal from the study or study drug.

Clinical laboratory data will be summarized by the type of laboratory test. For each clinical laboratory test, descriptive statistics will be provided on Baseline as well as all subsequent visits. Descriptive statistics for physical examination results and vital signs will also be provided.

Detailed statistical methods will be provided in the SAP.

Page 110

14.7 Determination of Sample Size

Approximately one hundred and thirty (130) subjects may be dosed in the study. The sample size for this study is based on clinical and statistical considerations in order to provide sufficient data to assess both safety and efficacy of BMN 270.

For the primary endpoint, a sample size of 130 will provide at least 95% power to demonstrate that the change in hFVIII activity during Weeks 49-52 from baseline is greater than 0, assuming an effect size of 0.6, using a one-sample t-test with a 2-sided significance level of 0.05. The effect size of 0.6 is assumed based on Study 270-201 data. In Study 270-201 cohort 6E13, the mean (SD) of FVIII activity (IU/dL) at Week 52 (based on median values in a 4-week window around Week 52) were estimated as 103.8 (62.4), with a 95% confidence interval for the mean of (46.1, 161.5). Using the lower limit of the confidence interval and assuming a baseline value of 1 (the largest value allowed per the study's inclusion/exclusion criteria), the effect size of change from baseline is approximately 0.7. For the sample size calculation, an effect size of 0.6 is assumed.

For the secondary endpoints, the analysis will be performed utilizing exogenous FVIII use and bleeding episode data from the 110 subjects whose baseline data will be prospectively collected for approximately 6 months in the non-interventional study 270-902, prior to their enrollment in Study 270-301. An analytic sample size of 110 will provide at least 95% power to demonstrate that the change in the annualized utilization (IU/kg) of exogenous FVIII replacement therapy during Week 5 to Week 52 post-BMN 270 infusion from the baseline is less than 0, assuming an effect size of 0.6 conservatively, using one-sample t-test with a 2-sided significance level of 0.05.

For the analytic sample size calculation of the second secondary endpoint, ABR, it is assumed that the pre- and post-BMN 270 infusion population mean ABRs are 3.5 and 1 respectively, and the distribution of ABRs is negative binomial distribution with a dispersion parameter of 2.2. Given the underlying negative binomial distributions, the standard deviations of the pre- and post-BMN 270 infusion ABRs are calculated as 7.8 and 1.8 respectively. The mean (SD) of the change from the pre- to post-BMN 270 infusion ABRs are calculated as -2.5 (8) assuming the correlation between pre- and post-BMN 270 infusion ABRs is zero. Under this assumption, an analytic sample size of 110 will also have at least 95% power to demonstrate that the change in the annualized number of bleeding episodes requiring exogenous FVIII replacement treatment (ABR) during Week 5 to Week 52 of the study post-BMN 270 infusion from the baseline ABR is less than 3.5 (non-inferiority margin), using a one-sample t-test with a 2-sided significance level of 0.05. Under the same assumptions, a sample size of 110 will have approximately 90% power to

Page 111

demonstrate that the change is less than 0, ie, superiority of BMN 270 against FVIII prophylaxis.

Overall, the planned sample size will have greater than 80% power for testing the primary and secondary efficacy endpoints hierarchically at the final analysis with a 2-sided significance level of 0.05.

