An analytic sample size of 110 will also have at least 95% power to demonstrate that the change in the annualized number of bleeding episodes requiring exogenous FVIII replacement treatment (ABR) during Week 5 to Week 52 of the study post-BMN 270 infusion from the baseline ABR is less than 3.5 (non-inferiority margin), assuming the pre- and post-BMN 270 infusion population mean ABRs are 3.5 and 1 respectively, using a one-sample t-test with a 2-sided significance level of 0.05. Under the same assumptions, a sample size of 110 will have approximately 90% power to demonstrate that the change is less than 0, i.e. superiority of BMN 270 against FVIII prophylaxis.

Overall, the planned sample size will have greater than 80% power for testing the primary and secondary efficacy endpoints hierarchically with a 2-sided significance level of 0.05.

Analysis Population

The intention-to-treat (ITT) population is defined as all subjects who receive BMN 270 infusion, and the modified intention-to-treat (mITT) population is defined as subjects who receive BMN 270 infusion and are HIV-negative. The mITT population will be used for the primary efficacy

NAME OF COMPANY	SUMMARY TABLE	FOR NATIONAL
BioMarin Pharmaceutical Inc.	Referring to Part of the	AUTHORITY USE
[name]	Dossier:	ONLY:
[name]		
	Volume:	
NAME OF FINISHED PRODUCT:		
BMN 270	Page:	
NAME OF ACTIVE INCREDIENT.		
NAME OF ACTIVE INGREDIENT:	Reference:	
AAV5-hFVIII-SQ		

analysis, and the ITT population will be used for the supportive efficacy analysis. The ITT population will also be used for the safety analysis.

Analysis

For the primary efficacy endpoint at Week 52 (ie, the change in the hFVIII activity during Weeks 49-52 post-BMN 270 infusion from baseline, as measured by chromogenic substrate assay), a one-sample t-test will be used to test the null hypothesis that the change is 0 or less against the alternative hypothesis that the change is greater than 0. Descriptive summaries of the proportions of subjects whose FVIII activity during Weeks 49-52 is greater than or equal to select thresholds, such as 15, 25 and 30 IU/dL, and the confidence intervals of the proportions will also be provided.

For the secondary endpoints, the analyses will be performed on 110 subjects in the mITT population whose baseline data will be prospectively collected for approximately 6 months in the non-interventional study 270-902 prior to their enrollment in 270-301.

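### The baseline ABR standard deviation of 7.8 does not follow from the stated negative binomial assumption, so the 90% superiority power holds only under an unstated variance step; on the stated assumptions it is about 99%

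*Protocol*

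**What the plan says.** Section 14.7 of the protocol (Amendment 4 text) sizes the ABR comparison as follows.

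- Means: "the pre- and post-BMN 270 infusion population mean ABRs are 3.5 and 1 respectively".
- Distribution: "the distribution of ABRs is negative binomial distribution with a dispersion parameter of 2.2".
- Standard deviations, presented as derived from that distribution: "the standard deviations of the pre- and post-BMN 270 infusion ABRs are calculated as 7.8 and 1.8 respectively".
- Change: mean -2.5 with SD 8, "assuming the correlation between pre- and post-BMN 270 infusion ABRs is zero".
- Test: "using a one-sample t-test with a 2-sided significance level of 0.05".
- Superiority: "a sample size of 110 will have approximately 90% power to" show a change below 0.

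The same section says that the baseline data for these 110 subjects are collected over about 6 months in study 270-902. The post-infusion rate covers Weeks 5 to 52. Section 14.3 plans a sensitivity analysis of bleeding counts with a negative binomial mixed model, using observation time as an offset.

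The Amendment 6 synopsis repeats the two means and the power: "Under the same assumptions, a sample size of 110 will have approximately 90% power to demonstrate that the change is less than 0". It gives no SD and no dispersion.

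**The concern.** One distribution, one dispersion parameter and two means should give both standard deviations. They give the post-infusion value but not the pre-infusion value. The pre-infusion SD contributes almost all of the variance of the change, so the SD of 8 and the 90% superiority power depend on it. That 90% is the lowest power quoted for any single test in the hierarchy; the others are quoted as at least 95%. A reader who tries to reproduce the sample-size justification from its stated inputs cannot do so, and cannot tell whether the dispersion, the SD or an omitted step is at fault.

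**Working it through.** **Inputs (section 14.7):** means 3.5 and 1; dispersion k = 2.2; correlation 0; n = 110; one-sample t-test, two-sided 0.05; baseline about 6 months; post-infusion window Weeks 5 to 52, about 48 weeks.

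**1. The plan's power from its own SDs.**
- SD of change = √(7.8² + 1.8²) = √(60.84 + 3.24) = 8.00. This agrees with the stated 8.
- Noncentrality = (2.5/8) × √110 = 3.28 on 109 degrees of freedom. Power by the noncentral t distribution is 90.1%, which agrees with the stated figure.

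Everything downstream of 7.8 is therefore correct.

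**2. The SDs from the stated distribution**, with variance = μ + kμ².
- Post-infusion: √(1 + 2.2 × 1²) = √3.2 = 1.79. This reproduces 1.8 and identifies the parameterization.
- Pre-infusion: √(3.5 + 2.2 × 3.5²) = √30.45 = 5.52, not 7.8.
- The other common form, μ + μ²/k, gives 3.01 and 1.21 and fits neither stated value.
- To reach 7.8 directly at mean 3.5, k must be (7.8² − 3.5)/3.5² = 4.68.

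**3. Does the 6-month baseline explain it?** The half-year mean is 1.75, and the annualized rate is twice the count.
- Dispersion held at 2.2: 2 × √(1.75 + 2.2 × 1.75²) = 2 × √8.4875 = 5.83.
- Whole variance doubled: √2 × 5.52 = 7.80, which matches 7.8. This is the same as a 6-month dispersion of 4.4: 2 × √(1.75 + 4.4 × 1.75²) = 2 × √15.225 = 7.80.
- The same scaling on a 48-week post-infusion window gives √(3.2 × 52/48) = 1.86, not the stated 1.8. Holding k at 2.2 over 48 weeks gives 1.81, which does agree.

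**4. Consequence for superiority** (change -2.5, n = 110, two-sided 0.05, noncentral t).

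| Pre-infusion SD | SD of change | Power |
|---|---|---|
| 7.8 (as stated) | 8.0 | 90.1% |
| 5.52 (one-year count, k = 2.2) | √(30.45 + 3.2) = 5.80 | 99.4% |
| 5.83 (6-month count, k = 2.2) | √(33.95 + 3.2) = 6.10 | 98.9% |

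Non-inferiority against the 3.5 margin (distance 6 from the assumed change) has power above 99.9% in all three rows.

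**5. Check on normality.** Simulated t-tests on negative binomial counts (20,000 trials each) gave power above 99.9% for the one-year count, 99.9% for the 6-month count with k = 2.2, and 98.2% for the doubled-variance version. Departure from normality does not reverse the direction.

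**The case against.** The strongest defence is that 7.8 is deliberate. Section 14.7 gives a baseline of about 6 months. If a negative binomial process has independent increments, annualizing a half-year count multiplies the one-year SD by exactly √2, which gives 7.80 and an SD of change of 8.01. Both stated figures are matched. The protocol does not say that dispersion stays constant when the observation period changes, so holding it at 2.2 is also a modelling choice. What stands of this is that 7.8 cannot be shown to be a slip of arithmetic.

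It does not rescue the text as written, for three reasons. The step appears nowhere, and the SDs are attributed to the negative binomial with dispersion 2.2 alone. It implies a 6-month dispersion of 4.4, whereas the negative binomial model with a time offset planned in section 14.3 leads to 5.83. It was also not applied to the post-infusion figure.

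Three stronger readings are tempting, and the documents support none of them.

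- A reader might infer that the power was miscalculated. It was not: 90.1% follows from an SD of 8.
- A reader might infer that the study was oversized. Section 14.7 rests the sample size on clinical as well as statistical considerations, including safety data, and not on this endpoint alone.
- A reader might infer that the surplus power bears on the 3.5 non-inferiority margin. The text shown does not justify the margin by power, and non-inferiority power is above 99.9% under every SD considered.

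The SD text is from Amendment 4. The Amendment 6 sample-size section is not in the supplied text. The Amendment 6 summary says sample size and final-analysis methods are unaffected, so the paragraph probably carries over, but this cannot be checked.

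**Conclusion.** The point holds as an inconsistency between a stated assumption and a stated result. With mean 3.5 and dispersion 2.2 the pre-infusion SD is 5.5 (one-year count) or 5.8 (annualized 6-month baseline), not 7.8. The SD of change is then 5.8 to 6.1, not 8, and superiority power at n = 110 is about 99%, not about 90%. The 90% is valid only conditionally on the SD of 8.

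This rests on variance = μ + kμ², which the post-infusion 1.8 confirms, on zero correlation as stated, and on the noncentral t approximation. That the whole variance was doubled is an inference from the numerical match.

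The discrepancy understates power. The 110-subject analysis set, the non-inferiority power and the overall claim of more than 80% for the hierarchy are unaffected.

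**What to change.** In the sample-size section (14.7 in Amendment 4; 14.8 in the Amendment 6 contents), do one of the following and carry the result into the synopsis.

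- Restate the pre-infusion SD as 5.8 with the 6-month exposure written out, the SD of change as about 6.1, and superiority power as about 99% with 110 subjects.
- If 7.8 is intended, state the variance-scaling assumption that produces it (equivalent to a 6-month dispersion of 4.4), say why it is not applied to the 48-week post-infusion period, and label the 90% as conditional on it.

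The cost is one paragraph and one synopsis sentence. Enrolment does not change; the Amendment 6 summary reports it complete.
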